APPENDIX 1: PROGRAMMING CONVENTIONS FOR OUTPUTS

OUTPUT CONVENTIONS

Outputs will be presented as shown in the Output shells.

DECIMALS, PERCENTAGES, AND P-VALUES

- If the original data has N decimal places, then the summary statistics should have the following decimal places:
 - Minimum and maximum: N
 - Mean (and LS Means), median: N + 1
 - SD or SE: N + 2
- Percentages will be reported to one decimal place. Where counts are zero, percentages will not appear in the output.
- P-values will be reported to three decimal places, except values < 1.000 but > 0.999 will be presented as ' > 0.999 ' (eg, 0.9998 is presented as > 0.999).
- Values < 0.001 will be presented as ' < 0.001 ' (eg, 0.0009 is presented as < 0.001). Rounding will be applied after the < 0.001 and > 0.999 rule.

CONVENTIONS RELATED TO PHARMACOKINETIC DATA

All etrasimod concentrations will be reported and analyzed with the same precision as the source data provided by the bioanalytical laboratory regardless of how many significant figures or decimals the data carry. The derived PK data (etrasimod concentration) will be rounded to carry 3 significant digits and considered the source data for the calculation of descriptive statistics and the statistical analysis source data.

For the reporting of descriptive statistics, the mean, geometric mean, median, SD, % CV, and % geometric CV will be presented with 4 significant digits. The minimum and maximum will be presented with 3 significant digits.

DATES AND TIMES

Depending on data available, dates and times will take the form DDMMYYYY or DDMMYYYY:hh:mm.

SPELLING FORMAT

English US.

PRESENTATION OF TREATMENT GROUPS

For outputs, treatment groups will be represented as follows and in that order:

Treatment Group	For Tables, Graphs, and Listings
Etrasimod	Etrasimod
Placebo	Placebo
Screen Failure	Screen Failure
Not Treated ^a	Not Treated

^a To be used for subjects in safety listings who are randomized but do not receive study treatment.

PRESENTATION OF VISITS AND STUDY PERIOD

For outputs, visits and study periods will be represented as follows and in that order:

Visit Name	Study Period
Screening	Screening
Baseline, Day 1, Week 2, Week 4, Week 8, Week 12, Week 16, Week 20, Week 24, Week 32, Week 40, Week 48, and Week 52	Treatment
End of Study/Early Termination	Dependent on Analysis Visit assigned, described in Section 6.4
2-Week Follow-Up, 4-Week Follow-Up	Follow-Up

LISTINGS

All listings will be ordered by the following (unless otherwise indicated in the template):

- Randomized treatment group (or treatment received if it is a safety output), first by Etrasimod, then Placebo, then Screen Failure and then No Treatment (only in safety listings if there are any randomized subjects who did not receive study treatment)
- Subject number (which is expected to incorporate study site/center)
- Date (where applicable)

APPENDIX 2: PARTIAL DATE CONVENTIONS

Imputed dates will NOT be presented in the listings.

ALGORITHM FOR TREATMENT EMERGENCE OF ADVERSE EVENTS:

AE Start Date	AE Stop Date	Action
Known	Known, Partial, or Missing	If AE start date < study treatment first dose date, then not TEAE If AE start date ≥ study treatment first dose date, then TEAE
Partial, but known components show that it cannot be on or after date of first dose of study treatment	Known, Partial, or Missing	Not TEAE
Partial, could be on or after date of first dose of study treatment	Known	If AE stop date < study treatment first dose date, then not TEAE If AE stop date ≥ study treatment first dose date, then TEAE
	Partial	Impute AE stop date as latest possible date (ie, last day of month if day unknown or 31st December if day and month are unknown), then: If AE stop date < study treatment first dose date, then not TEAE If AE stop date ≥ study treatment first dose date, then TEAE
	Missing	Assumed TEAE
Missing	Known	If AE stop date < study treatment first dose date, then not TEAE If AE stop date ≥ study treatment first dose date, then TEAE
	Partial	Impute AE stop date as latest possible date (ie, last day of month if day unknown or 31st December if day and month are unknown), then: If AE stop date < study treatment first dose date, then not TEAE If AE stop date ≥ study treatment first dose date, then TEAE
	Missing	Assumed TEAE

ALGORITHM FOR PRIOR AND CONCOMITANT MEDICATIONS:

Start Date	Stop Date	Action
Known	Known	If medication stop date < study treatment first dose date, assign as prior If medication stop date ≥ study treatment first dose date, assign as concomitant
	Partial	Impute stop date as latest possible date (ie, last day of month if day unknown or 31st December if day and month are unknown), then: If medication stop date < study treatment first dose date, assign as prior If medication stop date ≥ study treatment first dose date, assign as concomitant
	Missing	If medication stop date is missing could never be assumed a prior medication, assign as concomitant
Partial	Known	Impute start date as earliest possible date (ie, first day of month if day unknown or 1st January if day and month are unknown), then: If medication stop date < study treatment first dose date, assign as prior If medication stop date ≥ study treatment first dose date, assign as concomitant
	Partial	Impute start date as earliest possible date (ie, first day of month if day unknown or 1st January if day and month are unknown) and impute stop date as latest possible date (ie, last day of month if day unknown or 31st December if day and month are unknown), then: If medication stop date < study treatment first dose date, assign as prior If medication stop date ≥ study treatment first dose date, assign as concomitant
	Missing	Impute start date as earliest possible date (ie, first day of month if day unknown or 1st January if day and month are unknown), then: If medication stop date is missing could never be assumed a prior medication, assign as concomitant
Missing	Known	If medication stop date < study treatment first dose date, assign as prior Else assign as concomitant
	Partial	Impute stop date as latest possible date (ie, last day of month if day unknown or 31st December if day and month are unknown), then: If medication stop date < study treatment first dose date, assign as prior If medication stop date ≥ study treatment first dose date, assign as concomitant
	Missing	Assign as concomitant

ALGORITHM FOR STARTING DATE OF HOSPITALIZATION AND START/STOP DATES OF CONCOMITANT MEDICATIONS:

Start Date	Stop Date	Action
Partial	Partial	Impute start date as earliest possible date (ie, first day of month if day unknown or 1st January if day and month are unknown). Impute stop date to latest possible date (ie, last day of month if day unknown or 31st December if day and month are unknown). No partial stop date imputation for hospitalization.
Missing	Missing	Impute start date as informed consent date. Impute stop date as last visit date when the concomitant medication timepoint is not ongoing. No missing stop date imputation for hospitalization.

[REDACTED]

[REDACTED]

[REDACTED]

[REDACTED]

[REDACTED]

[REDACTED]

[REDACTED]

[REDACTED]

[REDACTED]

[REDACTED]

[REDACTED]

[REDACTED]

[REDACTED]

[REDACTED]

[REDACTED]

[REDACTED]

[REDACTED]

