9.10.8.1.5. Severity

The severity of each adverse event will be assessed at the onset by a nurse/or physician. When recording the outcome of the adverse event the maximum severity of the adverse event experienced will also be recorded. The severity of each adverse event will be graded according to the Common Terminology Criteria for Adverse Events, version 5.0 (CTCAE v5.0):

- | | |
|----------|----------------------------------------------------------------------------------------------------------------------------------------------------------------------------------------------------------------------------------------------------------------------|
| Grade 1: | Mild; asymptomatic or mild symptoms; clinical or diagnostic observations only; intervention not indicated. |
| Grade 2: | Moderate; minimal, local or noninvasive intervention indicated; limiting age-appropriate instrumental activities of daily living (ADL). |
| Grade 3: | Severe or medically significant but not immediately life-threatening; hospitalization or prolongation of hospitalization indicated; disabling, limiting self-care ADL (eg, preparing meals, shopping for groceries or clothes, using the telephone, managing money). |
| Grade 4: | Life-threatening consequences, urgent intervention indicated. |
| Grade 5: | Death related to adverse event. |

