9.10.8.2.2. Recording Adverse Events

The adverse event reporting period for safety surveillance begins when the subject is initially included in the study (date of first signature of informed consent) and continues up to 30 days after the last administration of study treatment. If an adverse event is not resolved or stabilized by this time, the Sponsor in consultation with the Investigator will decide whether to continue to monitor the adverse event or closeout the event in the database if no further follow-up is necessary.

Any SAE suspected to be related to the study treatment must be reported whenever it occurs, irrespective of the time elapsed since the last administration of study treatment.

Investigators and study personnel will record all adverse events and SAEs whether received through an unsolicited report by a subject, elicited during subject questioning, discovered during physical examination, laboratory testing, and/or other means by recording them on the eCRF and/or SAE Form, as appropriate. The following information should be recorded on the adverse event eCRF:

- Description including onset and resolution dates
- Whether it met SAE criteria
- Severity
- Relationship to study treatment or other causality
- Outcome

For SAEs, events occurring secondary to the primary event should be described on the eCRF in the narrative description field.

The following should be considered when recording SAEs:

- Death is an outcome of an event. The event that resulted in the death should be recorded and reported on the eCRF.
- For hospitalizations, surgical, or diagnostic procedures, the illness leading to the surgical or diagnostic procedure should be recorded as the SAE, not the procedure

itself. The procedure should be captured in the narrative as part of the action taken in response to the illness.

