18.1. Adverse Events

AEs will be coded using MedDRA (v24.1). The version used to code AEs will be displayed in the analyses. Treatment-emergent adverse events (TEAEs) are defined as AEs that started or worsened in severity on or after the first dose of study treatment.

Refer to [Appendix 2](#) for handling of partial dates for AEs for the purpose of assigning treatment-emergent flags. In the case where it is not possible to define an AE as treatment-emergent or not, the AE will be classified as treatment-emergent.

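### SAP 18.1 counts adverse events that worsen on treatment as TEAEs, but the Appendix 2 algorithm flags any event with a determinable pre-dose start as not TEAE and never tests for worsening

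*SAP*

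**What the plan says.** SAP Section 18.1 gives the definition: "Treatment-emergent adverse events (TEAEs) are defined as AEs that started or worsened in severity on or after the first dose of study treatment". It then refers to Appendix 2 "for handling of partial dates for AEs for the purpose of assigning treatment-emergent flags" and adds a default: "In the case where it is not possible to define an AE as treatment-emergent or not, the AE will be classified as treatment-emergent".

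The first table in Appendix 2 is titled as the algorithm for treatment emergence. It uses only the start and stop dates of the event. Two of its rows concern events that began before treatment:

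- **Start date known.** "If AE start date < study treatment first dose date, then not TEAE", whatever is known about the stop date.
- **Start date partial.** The row for a date described as "Partial, but known components show that it cannot be on or after date of first dose of study treatment" returns not TEAE, again whatever the stop date.

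The remaining rows cover ambiguous partial or missing start dates. They return TEAE when the stop date is on or after first dose, or is missing.

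Two protocol rules determine which records reach this algorithm. Section 9.10.8.2.2 starts collection at consent: "The adverse event reporting period for safety surveillance begins when the subject is initially included in the study". The same section lists onset and resolution dates for the adverse event form, but no date of worsening. Section 9.10.8.1.5 has severity assessed at onset and then says: "When recording the outcome of the adverse event the maximum severity of the adverse event experienced will also be recorded".

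**The concern.** The definition has two limbs, started and worsened. The algorithm implements only the first, and for a determinable pre-dose start it returns a definite negative.

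Screening normally lasts 28 days and can be extended (protocol Section 9.3), so events with a pre-dose start are to be expected. If such an event is mild in screening and becomes severe or serious on treatment within the same record, it is absent from the summaries that use the flag:

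- system organ class and preferred term tables, and exposure-adjusted rates (SAP 18.1.1)
- maximum severity and related events (18.1.1.1, 18.1.1.2)
- discontinuations (18.1.2) and serious events (18.1.3)
- the special-interest tables and recurrent-event Cox model (18.1.5)
- the overview and the TEAE-based risk differences (18.1.6)

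If treatment aggravates events that are already present, this omission removes exactly the records that would show it.

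**Working it through.** The plan states no figure on this point, so the check is to apply both rules to the same event patterns. In the examples below, a pre-dose start means 10 days before first dose unless the start is described as partial or missing, and worsening means a higher grade on Day 20.

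| Event pattern | Appendix 2 | Section 18.1 | Agree? |
|---|---|---|---|
| 1. Known pre-dose start, worsens, resolves Day 40, one record | not TEAE | TEAE | no |
| 2. Known pre-dose start, worsens, ongoing, one record | not TEAE | TEAE | no |
| 3. Partial start that must be pre-dose, worsens, one record | not TEAE | TEAE | no |
| 4. Ambiguous partial start (truly pre-dose), worsens, stops Day 40 | TEAE | TEAE | yes |
| 5. Start and stop both missing (truly pre-dose start), worsens | TEAE | TEAE | yes |
| 6. Worsening entered as a new record starting Day 20 | TEAE | TEAE | yes |
| 7. Known pre-dose start, no worsening | not TEAE | not TEAE | yes |

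The rules conflict in patterns 1 to 3, where the start is determinable as pre-dose and the worsening sits in the same record. They agree in the other four.

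**Does the Section 18.1 default rescue patterns 1 to 3?** No. It applies only when emergence cannot be determined, and here the algorithm gives a definite answer.

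**Do the documents put worsening in a new record?** No passage requires that for an event already recorded. Recording maximum severity with the outcome of an event, and listing only onset and resolution dates, both point to a single record. Neither forbids a second one.

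**Does changing the flag alone suffice?** No. SAP 18.1.1 measures exposure from first dose to onset of the event, and the Cox model in 18.1.5 measures from time 0 to the event start date. A record that started 10 days before first dose would contribute a time of about -10 days to both, so a usable event date is needed as well.

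**The case against.** The best defence is that Section 18.1 is the operative definition and calls on Appendix 2 only for partial dates, as the appendix title suggests. On that reading the table serves the started limb and the worsened limb still applies separately. The explicit row for known start dates defeats this, because a partial-date convention would not need one. The table is also titled as the algorithm for emergence, and a programmer who follows it will flag fully dated events by start date alone. It is fair to add that the programming specification is not among the documents, so the final code may differ.

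A second defence is that single-record entry is inferred. This stands in part. The form and its completion instructions are not in the documents, and sites may have split records. Protocol Section 9.10.8.1.1 also makes a worsened pre-existing condition an adverse event in its own right, and such an event entered with an on-treatment onset is counted.

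A reader might infer three stronger things that the documents do not support:

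- *That every event beginning before first dose is excluded, or that all on-treatment worsening is lost.* Patterns 4 to 6 show otherwise.
- *That all safety tables are affected.* Laboratory, ECG, vital-sign, pulmonary function and ophthalmic summaries do not use the flag. The all-event listing keeps every record. For special-interest events, SAP 18.1.5 also has test data reviewed for cases that investigators missed.
- *That a percentage can be attached.* The affected share of subjects is the proportion with an event ongoing at first dose times the proportion of those that worsen. Assuming 5% to 20% and 10% to 30% gives 0.05 x 0.10 = 0.5% up to 0.20 x 0.30 = 6%. Neither input is in the documents, so this range is an illustration and not an estimate.

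**Conclusion.** The inconsistency is real. For an adverse event whose start is known, or determinable from a partial date, to precede first dose, and which worsens on treatment within the same record, Appendix 2 gives a flag that contradicts Section 18.1. Such events drop out of the TEAE-based summaries while staying in the listing.

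The practical effect depends on one assumption: that sites recorded worsening within the existing record. Protocol Section 9.10.8.1.5 suggests this but does not settle it. The size of the effect, and any imbalance between arms, cannot be computed from the documents. No efficacy endpoint is touched. It is still worth correcting, because the omission works against detecting aggravation of existing events by treatment.

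**What to change.** Either of two changes resolves it.

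**Option 1: amend Appendix 2.** In the two pre-dose rows, classify an event that was ongoing at first dose as TEAE if its severity increased on or after first dose.

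- Take an increase to mean that maximum severity exceeds the grade at onset. This requires both grades to be in the database, which should be confirmed.
- If the timing of the increase is unknown, treat it as on or after first dose. This follows the direction of the Section 18.1 default.
- For the exposure-adjusted rates and the Cox model, use the date of worsening as the event start. If that date was not recorded, use the first-dose date and handle it as any event that starts on the day of first dose.

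**Option 2: state the recording rule.** Say in the SAP that on-treatment worsening is entered as a new adverse event record with its own start date, and verify before unblinding that the data were collected that way. Appendix 2 can then stand, because each worsening has an on-treatment start.

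**Cost.** Option 1 needs a short change to two table rows, an event-date rule in Sections 18.1.1 and 18.1.5, and the matching programming. Its downside is that a few events that peaked during screening may be counted as TEAEs, though the same rule applies in both arms. Option 2 needs a sentence in the SAP and a blinded data check. If the check shows that sites did not split records, Option 1 is needed after all.

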APPENDIX 4: IBDQ SCORING RULES

The Inflammatory Bowel Disease Questionnaire (IBDQ) is a 32-item self-administered questionnaire which has 4 dimensions: Bowel symptoms (10 items), systemic symptoms (5 items), emotional health (12 items), and social function (5 items). Responses are graded on a 7-point Likert scale where 7 denotes “not a problem at all” and 1 denotes “a very severe problem”. Scores range from 32 to 224, a higher score indicates better quality of life.

The 4 dimensions are defined as:

- Bowel symptoms: Questions 1, 5, 9, 13, 17, 20, 22, 24, 26, 29
- Systemic symptoms: Questions 2, 6, 10, 14, 18
- Emotional health: Questions 3, 7, 11, 15, 19, 21, 23, 25, 27, 30, 31, 32
- Social function: Questions 4, 8, 12, 16, 28

APPENDIX 5: SF-36 SCORING RULES

The Medical Outcomes Study 36 Item Short Form Health Survey (SF-36) is a 36-item self-administered questionnaire which has 8 scales: Physical functioning (10 items), role limitations due to physical health (4 items), role limitations due to emotional problems (3 items), vitality (4 items), mental health (5 items), social functioning (2 items), bodily pain (2 items), and general health (5 items). Each item response is scored from 0 to 100 and items in the same scale are averaged together to create 8 subscores. Scores range from 0 to 100. A higher score indicates a more favorable health state.

The 8 dimensions are defined as:

- Physical functioning: Questions 3 to 12
- Role limitations due to physical health: Questions 13 to 16
- Role limitations due to emotional problems: Questions 17 to 19
- Vitality: Questions 23, 27, 29, 31
- Mental health: Questions 24 to 26, 28, 30
- Social functioning: Questions 20, 32
- Bodily Pain: Questions, 21, 22
- General health: Questions 1, 33 to 36

APPENDIX 6: WPAI-UC SCORING RULES

The Work Productivity and Activity Impairment Questionnaire – Ulcerative Colitis (WPAI-UC) questionnaire was developed to measure the effect of general health and symptom severity on work productivity and regular activities. The questionnaire includes the following questions.

Questions:

- 1 = Are you currently employed?
- 2 = During the past seven days, how many hours did you miss from work due to your problems associated with UC?
- 3 = During the past seven days, how many hours did you miss from work because of any other reasons?
- 4 = During the past seven days, how many hours did you actually work?
- 5 = During the past seven days, how much did your UC affect your productivity while you were working?
- 6 = During the past seven days, how much did your UC affect your ability to do your regular daily activities, other than work at a job?

Derivation:

- 1) Calculate work time missed score as: $Q2/(Q2 + Q4)$
- 2) Calculate impairment while working score as: $Q5/10$
- 3) Calculate overall work impairment score as: $Q2/(Q2 + Q4) + [(1 - Q2/(Q2 + Q4)) \times (Q5/10)]$
- 4) Calculate activity impairment score as: $Q6/10$

Multiply each score by 100 in order to express as percentages.

APPENDIX 7: CLASSIFICATION OF RESCUE THERAPY

This appendix outlines the algorithm for the Arena clinical team/medical reviewers to classify rescue therapies for ulcerative colitis (UC) in a blinded manner. This will help establish 1) intercurrent events for the efficacy estimands, and 2) whether a subject will be excluded from the Per Protocol Set(s). All rescue therapies identified by the medical reviewers per the algorithm below will be imported in programming. This process will be repeated until database lock and the list of all rescue therapies identified will be finalized before study unblinding.

Only medications and medical procedures reported on the electronic case report forms (eCRFs) can be assessed whether they are rescue therapy for UC. If the exposure happens in the follow-up period (beginning on or after the date of last study treatment administration), then it would not be considered as a rescue therapy. Impact of rescue therapy use in the analysis is timing-dependent, eg, if a subject starts a rescue therapy between their Week 12 and Week 52 endpoint assessments, then it may have potential impact on Week 52 endpoint analysis but will have no impact on Week 12 endpoints. The rules outlined below apply to both new use and increase in dose from Baseline.

Biologics with immunomodulatory properties

- Rule:
 - Any exposure after first dose
- List of medications:
 - AntiTNF α antibodies:
 - ADALIMUMAB
 - CERTOLIZUMAB
 - CERTOLIZUMAB PEGOL
 - GOLIMUMAB
 - INFLIXIMAB
 - Other Biologics:
 - USTEKINUMAB
 - VEDOLIZUMAB

Nonbiologics with immunomodulatory properties

- Immunosuppressants
 - Rules to consider for Week 12 efficacy endpoints:
 - After first dose and up to and including Week 8: any increase from baseline for more than 5 days
 - After Week 8: Any dose above baseline

-
- Rules to consider for Week 52 efficacy endpoints:
 - After Week 12 and up to and including Week 40: any increase from baseline for more than 5 days
 - After Week 40: Any dose above baseline
 - List of medications:
 - MERCAPTOPYRINE
 - AZATHIOPRINE
 - TIOGUANINE
 - METHOTREXATE
 - METHOTREXATE SODIUM
 - 5-ASA COMPOUNDS
 - Rules to consider for Week 12 efficacy endpoints:
 - After first dose and up to and including Week 8: any increase from baseline for more than 5 days
 - After Week 8: Any dose above baseline
 - Rules to consider for Week 52 efficacy endpoints:
 - After Week 12 and up to and including Week 40: any increase from baseline for more than 5 days
 - After Week 40: Any dose above baseline
 - List of medications:
 - MESALAZINE
 - BALSALAZIDE
 - BALSALAZIDE DISODIUM DIHYDRATE
 - BALSALAZIDE SODIUM
 - OLSALAZINE SODIUM
 - SULFASALAZINE
 - BECLOMETASONE W/MESALAZINE
 - Routes:
 - ORAL
 - RECTAL
 - Other small molecule immunomodulatory active agents
 - Rules to consider for Week 12 efficacy endpoints:

-
- After first dose and up to and including Week 8: any increase from baseline (including new use) for more than 5 days
 - After Week 8: Any dose above baseline
 - Rules to consider for Week 52 efficacy endpoints:
 - After Week 12 and up to and including Week 40: any increase from baseline (including new use) for more than 5 days
 - After Week 40: Any dose above baseline
 - List of medications:
 - CICLOSPORIN
 - TACROLIMUS
 - TOFACITINIB
 - TOFACITINIB CITRATE
 - Systemic glucocorticoids
 - Systemic glucocorticoids given via oral or rectal routes of administration
 - Rules to consider for Week 12 efficacy endpoints:
 - After first dose and up to and including Week 8: any increase from baseline for more than 7 days
 - After Week 8: Any dose above baseline
 - Rules to consider for Week 52 efficacy endpoints:
 - After Week 12 and up to and including Week 40: any increase from baseline for more than 7 days
 - After Week 40: Any dose above baseline
 - List of medications:
 - BETAMETHASONE
 - BETAMETHASONE DIPROPIONATE
 - BETAMETHASONE SODIUM PHOSPHATE
 - DEXAMETHASONE
 - DEXAMETHASONE SODIUM PHOSPHATE
 - DEXAMETHASONE VALERATE
 - METHYLPREDNISOLONE
 - METHYLPREDNISOLONE SODIUM SUCCINATE
 - PREDNISOLONE

-
- PREDNISOLONE SODIUM PHOSPHATE
 - PREDNISOLONE METASULFOBENZOATE SODIUM
 - PREDNISON
 - TRIAMCINOLONE
 - HYDROCORTISONE
 - HYDROCORTISONE ACETATE
 - HYDROCORTISONE BUTYRATE
 - HYDROCORTISONE SODIUM SUCCINATE
 - Routes:
 - ORAL
 - RECTAL
 - Systemic glucocorticoids given via parenteral routes of administration
 - Rule for Week 12 endpoint:
 - Any exposure after first dose up to Week 12
 - Rules for Week 52 endpoint:
 - After Week 12 and up to and including Week 40: more than one dose
 - Any exposure after Week 40
 - List of medications:
 - BETAMETHASONE
 - BETAMETHASONE DIPROPIONATE
 - BETAMETHASONE SODIUM PHOSPHATE
 - DEXAMETHASONE
 - DEXAMETHASONE SODIUM PHOSPHATE
 - DEXAMETHASONE VALERATE
 - METHYLPREDNISOLONE
 - METHYLPREDNISOLONE SODIUM SUCCINATE
 - PREDNISOLONE
 - PREDNISOLONE SODIUM PHOSPHATE
 - PREDNISOLONE METASULFOBENZOATE SODIUM
 - PREDNISON
 - TRIAMCINOLONE

-
- HYDROCORTISONE
 - HYDROCORTISONE ACETATE
 - HYDROCORTISONE BUTYRATE
 - HYDROCORTISONE SODIUM SUCCINATE
 - Routes:
 - INTRAVENOUS
 - INTRAMUSCULAR
 - Topical Glucocorticoids
 - Rules for Week 12 endpoints:
 - After first dose and up to and including Week 8: any exposure above baseline (or new use) for more than 5 days
 - After Week 8: Any dose above baseline
 - Rules for Week 52 endpoints:
 - After Week 12 and up to and including Week 40: any increase from baseline for more than 5 days
 - After Week 40 any increase above baseline
 - List of medications:
 - BUDESONIDE
 - Routes:
 - ORAL
 - RECTAL
 - Beclomethasone
 - Rules for Week 12 endpoints:
 - After first dose and up to and including Week 8: Any increase above baseline for more than 5 days
 - After Week 8: Any dose above baseline
 - Rules for Week 52 endpoints:
 - After Week 12 and up to and including Week 40: Any increase from baseline for more than 5 days
 - After Week 40 any increase above baseline
 - List of medications:
 - BECLOMETASONE

- BECLOMETASONE DIPROPIONATE
- BECLOMETASONE W/MESALAZINE
- Routes:
 - ORAL
 - RECTAL

Medical procedures

- Leukocyte apheresis, other apheresis, and plasma exchange
 - Rule:
 - Any exposure after first dose
 - List of medical procedures
 - APHERESIS
 - LEUKAPHERESIS
 - COLECTOMY (partial or total)
 - SIGMOIDECTOMY
 - COLOSTOMY
 - ILEOSTOMY

Statistical Analysis Plan - V1.0 - SAP or PK-PD Sections Thereof - 19-Jan-2022

Electronic Signature Manifestation

This page is a manifestation of the electronic signature(s) used in compliance with the organization's electronic signature policies and procedures.

Signer Full Name	Meaning of Signature	Date and Time
██████████	Document Approval (I certify that I have the education, training and experience to perform this task)	19 Jan 2022 20:47:12 UTC
██████████	Document Approval (I certify that I have the education, training and experience to perform this task)	19 Jan 2022 20:49:35 UTC
██████████	Document Approval (I certify that I have the education, training and experience to perform this task)	19 Jan 2022 20:50:35 UTC
██████████	Document Approval (I certify that I have the education, training and experience to perform this task)	19 Jan 2022 20:52:31 UTC
